7.3.5. Renal-related Laboratory Evaluations

7.3.5.1. Serum Creatinine and eGFR_{CG}

Baseline, postbaseline, and change from baseline in serum creatinine and eGFR_{CG} will be summarized by treatment group and visit using descriptive statistics.

Median (Q1, Q3) of change from baseline in serum creatinine and eGFR_{CG} over time will be plotted.

7.4. Body Weight, Height, and Vital Signs

Descriptive statistics will be provided by treatment group for body weight, BMI and vital signs as follows:

- Baseline value
- Values at each postbaseline analysis window
- Change from baseline at each postbaseline analysis window.

A baseline value will be defined as the last available value collected on or prior to the date/time of first dose of study drug. Change from baseline to a postbaseline visit will be defined as the postbaseline value minus the baseline value.

In the case of multiple values in an analysis window, data will be selected for analysis as described in Section 3.7.4. No formal statistical testing is planned.

A by-participant listing of vital signs will be provided by participant ID number and visit in chronological order. Body weight, height, and BMI will be included in the vital signs listing, if space permits. If not, they will be provided separately.

7.5. Prior and Concomitant Medications

Medications collected at screening and during the study will be coded using the current version of the World Health Organization (WHO) Drug dictionary.

7.5.1. Nonstudy Drug Antiretroviral Medications

Any nonstudy drug ARV medications used prior to, during, or after the study (if collected) will be coded using the Gilead-modified World Health Organization (WHO) Drug Dictionary for

ARV medications. All nonstudy drug ARV medications will be listed. Post study ARVs after participants who prematurely discontinued or completed the study drug (B/F/TAF) will be summarized.

7.5.2. Concomitant Non-ARV Medications

Concomitant non-ARV medications (ie, medications other than study drug that are taken while receiving study drug) will be coded using the WHO Drug Dictionary. Use of concomitant medications from Study Day 1 for All B/F/TAF analysis up to the date of last dose of study drug will be summarized (number and percentage of subjects) by drug class, and preferred drug name. Multiple drug use (by preferred drug name) will be counted only once per subject. The summary will be sorted by decreasing total frequency of preferred drug name. For drug with the same frequency, sorting will be done alphabetically.

For the purposes of analysis, any medications with a start date prior to or on the first dosing date of study drug and continued to be taken after the first dosing date or started after the first dosing date but prior to or on the last dosing date of study drug will be considered concomitant medications. Medications started and stopped on the same day as the first dosing date or the last dosing date of study drug will also be considered concomitant. Medications with a stop date prior to the date of first dosing date of study drug or a start date after the last dosing date of study drug will be excluded from the concomitant medication summary. If a partial stop date is entered, any medication with the month and year (if day is missing) or year (if day and month are missing) prior to the date of first study drug administration will be excluded from the concomitant medication summary. If a partial start date is entered, any medication with the month and year (if day is missing) or year (if day and month are missing) after the study drug stop date will be excluded from the concomitant medication summary. Medications with completely missing start and stop dates will be included in the concomitant medication summary, unless otherwise specified. Summaries will be based on the Safety Analysis Set. No formal statistical testing is planned.

Summaries of non-ARV concomitant medications will be provided for the Safety Analysis Set. Participants with any concomitant non-ARV medications will be listed. No inferential statistics will be provided.

7.6. Other Safety Measures

A by-participant listing of participant pregnancies during the study will be provided by participant ID number.

Although not necessarily related to safety, a by-participant listing of all comments received during the study on the comments form will be provided by participant ID number, and form for which the comment applies.

7.7. Changes From Protocol-Specified Safety Analyses

There are no deviations from the protocol-specified safety analyses.

8. PHARMACOKINETIC (PK) ANALYSES

PK samples will be collected for only participants from Northern American sites. French participants will not be included as part of the planned PK analysis.

8.1. PK Analysis Endpoint

The PK analysis endpoint which is included as part of secondary endpoint of this study is:

- Plasma concentration of BIC, CAB, and RPV at Day 1, Weeks 4, 12 and 24, as appropriate.

8.2. Trough and Single Postdose PK Sample Collection

A single PK plasma sample will be collected at Day 1 prior to dose. A single trough plasma PK sample approximately 23 to 24 hours after the previous B/F/TAF dose and prior to B/F/TAF dosing on Weeks 4, 12, and 24, and a single plasma PK sample at approximately 2 hours post B/F/TAF dose, witnessed by study staff, at Weeks 4, 12, and 24 will be collected.

8.3. PK Analyses on Trough and Postdose PK Concentrations

Natural logarithmic transformations will be used for analyzing plasma concentrations of BIC, CAB and RPV. Concentration values (including trough and postdose PK concentration) that are below the lower limit of quantitation (BLQ) will be presented as “BLQ” in the concentration listing and will be treated as zero at each time point for summary purposes.

The following conventions will be used for the presentation of order statistics and summary statistics for the PK concentration:

- If at least 1 participant has a concentration value of BLQ for the time point, the minimum value will be displayed as “BLQ.”
- If more than 25% of the participants have a concentration value of BLQ for a given time point, the minimum and Q1 values will be displayed as “BLQ.”
- If more than 50% of the participants have a concentration value of BLQ for a given time point, the minimum, Q1, and median values will be displayed as “BLQ.”
- If more than 75% of the participants have a concentration value of BLQ for a given time point, the minimum, Q1, median, and Q3 values will be displayed as “BLQ.”
- If all participants have concentration values of BLQ for a given time point, all order statistics (minimum, Q1, median, Q3, and maximum) and summary statistics will be displayed as “BLQ.”

Individual participant PK concentration data, including CAB and RPV for Day 1 (pre-dose), as well as BIC, CAB, and RPV for sparse trough and postdose PK concentrations will be listed and summarized at each time point for each analyte (as applicable) using descriptive statistics for subjects in the PK analysis set. The descriptive statistics (sample size, mean, SD, coefficient of variation [% CV], minimum, median, maximum, Q1, and Q3), will be presented for plasma concentration data. For concentration values BLQ, the number of subjects with values of BLQ will be presented.

The following tables will be provided for each analyte (ie, BIC, CAB, and RPV) using the associated PK Analysis Set:

- Individual participant concentration data and summary statistics at all protocol-specified PK sampling time points for each analyte (as applicable).

The following figures may be provided for each analyte (ie, BIC, CAB, and RPV) using the associated PK Analysis Set as appropriate:

- Mean (\pm SD) concentration data versus time (on linear and semilogarithmic scales). If more than one-third of the values at a postdose timepoint are BLQ or less than 5 participants presented at the timepoint then the mean and SD will not be presented at that time point and remaining points connected. If lower error bar (mean-SD) is < 0 at a timepoint then it will not be presented at that timepoint.
- Median (Q1, Q3) concentration data versus time (on linear and semilogarithmic scales). If more than one-third of the values at a postdose timepoint are BLQ or less than 5 participants presented at the timepoint then the median and quartile values will not be presented at that timepoint, and remaining points connected. If lower error bar (Q1) is BLQ at a timepoint then it will be presented as lower LOQ at that timepoint.

The following listings will be provided:

- PK sampling details by participant, including procedures, differences in scheduled and actual draw times, and sample age from the PK samples. Day1 (pre-dose), trough PK samples and postdose PK samples will be marked separately in the listing.

8.4. Sensitivity Analysis

A sensitivity analysis will be conducted by only including the participants who have received the study drugs per the protocol. In this scenario, the PK data will be presented as the overall summary and based on data from the participants that have received the study drugs per the protocol as part of the sensitivity analysis. Specifically, for participants who were on CAB+RPV IM injections twice monthly (Q2M) prior to enrollment but received first dose of the study drug (B/F/TAF) < 46 days of the last dose of CAB+RPV IM injection, their PK data will be excluded from the summary statistics in the sensitivity analysis.

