**Diagnosis and Main Eligibility Criteria:**

Medically stable HIV-1 infected participants who meet the following criteria:

- Age  $\geq$  18 years
- PWH or provider decision to switch off CAB+RPV due to intolerance, inconvenience, adverse events (AEs) or willing to switch to (and intention to remain on) daily B/F/TAF.
- Currently virologically suppressed (HIV-1 RNA  $< 50$  copies/ mL) on CAB+RPV IM injections (Q2M)
- Currently on CAB+RPV IM injections (Q2M) and received at least one dose of CAB+RPV IM injection; no missed CAB+RPV injections
- No immediate oral antiretroviral therapy (ART) bridge or use of other antiretroviral (ARV) agents before switching to B/F/TAF
- B/F/TAF to be given up to 7 days of next scheduled CAB+RPV IM injection
- Documented plasma HIV-1 RNA  $< 50$  copies/mL during treatment for  $\geq 6$  months preceding the screening visit. Unconfirmed HIV-1 RNA  $\geq 50$  copies/mL (transient detectable viremia, or “blip”) prior to screening are acceptable. If the lower limit of detection of the local HIV-1 RNA assay is  $< 50$  copies/mL (eg,  $< 20$  copies/mL), the HIV-1 RNA level cannot exceed 50 copies/mL on 2 consecutive visits.
- Estimated GFR  $\geq 30$  mL/min according to the Cockcroft-Gault formula
- No history of B/F/TAF intolerance
- No history of previous integrase strand-transfer inhibitor (INSTI) virologic failure including CAB+RPV
- No documented or suspected resistance to BIC, FTC, or tenofovir (TFV)
- Women who are not pregnant or breastfeeding
- In the opinion of the investigator, no history of poor adherence to oral daily medication

---

---

**Test Product, Dose, and Mode of Administration:** bictegravir 50 mg/emtricitabine 200 mg/tenofovir alafenamide 25 mg (B/F/TAF) FDC administered orally, once daily, without regard to food.

**Reference Therapy, Dose, and Mode of Administration:** None

**Duration of Intervention:** 24 weeks

---

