### 4.2. Inclusion Criteria

Participants must meet all of the following inclusion criteria to be eligible for participation in this study:

- 1) Participants 18 years of age or older and able to understand and give written informed consent.
- 2) PWH or provider decision to switch off CAB+RPV IM injections due to intolerance, inconvenience, AEs, *or* willing to switch to (and intention to remain on) daily B/F/TAF.
- 3) Currently virologically suppressed (HIV-1 RNA < 50 copies/mL) on CAB+RPV IM injections (Q2M).
- 4) Currently on CAB+RPV IM injections (Q2M) and received at least one dose of CAB+RPV IM injection; no missed CAB+RPV injections
- 5) Ability to receive B/F/TAF up to 7 days prior to the next scheduled dose of CAB+RPV.
- 6) Documented plasma HIV-1 RNA < 50 copies/mL during treatment for  $\geq$  6 months preceding the screening visit.
  - a) Unconfirmed HIV-1 RNA  $\geq$  50 copies/mL (transient detectable viremia, or “blip”) prior to screening are acceptable.
  - b) If the lower limit of detection of the local HIV-1 RNA assay is < 50 copies/mL (eg, < 20 copies/mL), the HIV-1 RNA level cannot exceed 50 copies/mL on 2 consecutive visits.

7) Adequate renal function

Estimated GFR  $\geq 30$  mL/min according to the Cockcroft-Gault formula {Cockcroft 1976} based on serum creatinine and actual body weight as measured at screening and upon admission, eg,

a) Male:

$$\frac{(140 - \text{Age [years]}) \cdot (\text{Weight [kg]})}{72 \cdot (\text{Serum Creatinine [mg/dL]})} = \text{CLcr (mL/min)}$$

b) Female:

$$\frac{(140 - \text{Age [years]}) \cdot (\text{Weight [kg]})}{72 \cdot (\text{Serum Creatinine [mg/dL]})} \times 0.85 = \text{CLcr (mL/min)}$$

8) Participants assigned female at birth of childbearing potential who engage in heterosexual intercourse must agree to use protocol-specified method(s) of contraception as described in Appendix 11.5.

9) Hepatic transaminases (AST and ALT)  $\leq 5 \times$  upper limit of normal (ULN)

10) Total bilirubin  $\leq 1.5$  mg/dL ( $\leq 26$   $\mu$ mol/L), or normal direct bilirubin.

11) No documented or suspected resistance to BIC, FTC, or tenofovir (TFV).

12) Must be willing and able to comply with all study requirements.

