Not needing to remember to take daily oral medication	 (h)
Fear of missing doses of daily oral HIV medications	 (i)
Wanting to forget about having HIV for a while (no reminder every day)	 (j)
More convenient than oral treatment	 (k)
I think injections would work better than daily oral medication	 (l)
It is a new and exciting HIV treatment	 (m)
Want to have more in-person contact with healthcare system	 (n)
Other reason ( described in the box below Question 2 )	 (y)

4. During your time taking CAB + RPV (Cabenuva), how inconvenient was it to go to the clinic/doctor's office to receive CAB + RPV (Cabenuva) injections as directed?

*Please check the  
one best answer*

Not at all inconvenient	 (a)
A little inconvenient	 (b)
Moderately inconvenient	 (c)
Very inconvenient	 (d)
Extremely inconvenient	 (e)

Participant ID Number: \_\_\_\_\_ Date of Survey: (month/day/year) \_\_\_\_\_

5. Did you reschedule any appointments for getting your CAB + RPV (**Cabenuva**) injections in the past 6 months?

*Please check the one best answer.*

I did not reschedule any appointments	 (a)
I rescheduled 1-2 appointments	 (b)
I rescheduled 3-4 appointments	 (c)
I rescheduled 5 or more appointments	 (d)

6. Did you miss any appointments entirely for getting your CAB + RPV (**Cabenuva**) injections in the past 6 months?

*Please check the one best answer.*

I did not miss any appointments	 (a)
Missed 1-2 appointments	 (b)
Missed 3-4 appointments	 (c)
Missed 5 or more appointments	 (d)

*Skip to Question 8*

Participant ID Number: \_\_\_\_\_ Date of Survey: (month/day/year) \_\_\_\_\_

7. Did missing appointments in the last 6 months lead to receiving CAB + RPV (**Cabenuva**) injections late or outside of the window when you were supposed to receive them?

Please check the one best answer.	
Yes	 (a)
No	 (b)
I don't know	 (c)

8. Which of the following side effects did you experience while on CAB + RPV (**Cabenuva**)?

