4.3. Protocol Deviations

If there are any participants did not meet the eligibility criteria for study entry but enrolled in the study, then will be summarized regardless of whether they were exempted by the sponsor or not. The summary will present the number and percentage of participants who did not meet at least 1 eligibility criterion and the number of participants who did not meet specific criteria by treatment group based on the All Enrolled Analysis Set. A by-participant listing will be provided for those participants who did not meet at least 1 eligibility (inclusion or exclusion) criterion. The listing will present the eligibility criterion (or criteria if more than 1 deviation) that participants did not meet and related comments, if collected.

Protocol deviations occurring after participants entered the study are documented during routine monitoring. The number and percentage of participants with at least 1 important protocol deviation will be summarized by deviation category for the All Enrolled Analysis Set as appropriate. The total number of important protocol deviations will be summarized by deviation category A by-participant listing will be provided for those participants with protocol deviations, included a column specify whether the protocol deviation is important.

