5.2. Other Baseline Characteristics

The following baseline disease characteristics will be summarized by overall using descriptive statistics for continuous variables and using number and percentage of participants for categorical variables.

- HIV-1 RNA categories (copies/mL): (a) < 50, (b) ≥ 50
- CD4 cell counts (/uL)
- CD4 cell counts categories (/uL): (a) < 50, (b) ≥50 to < 200, (c) ≥ 200 to < 350, (d) ≥ 350 to < 500, and (e) ≥ 500
- CD4 percentage (%)
- Mode of infection (HIV infection risk factors)
- HIV disease status: AIDS, asymptomatic, or symptomatic HIV infection
- eGFR_{CG} (mL/min)
- HBV Surface Antigen Status
- HBV Core Antibody Status
- HCV Antibody Status
- Duration of baseline CAB+RPV exposure (year)
- Time between last dose date of baseline CAB+RPV and first dose date of study drug (days)
- Historical HIV-1 genotype resistance results: INSTI (Yes/No/Data Not Available), NNRTI (Yes/No/Data Not Available), NRTI (Yes/No/Data Not Available), PI (Yes/No/Data Not Available).

These baseline characteristics will be summarized using descriptive statistics (n, mean, SD, median, Q1, Q3, minimum, and maximum) for continuous data and using number and percentage of participants for categorical variables. The summary of these baseline characteristics will be provided for the Safety Analysis Set. No formal statistical testing is planned.

A by-participant listing of other baseline characteristics will be provided by participant ID number in ascending order.

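### Does the 46-day cut-off in the PK sensitivity analysis clash with the protocol's switch window?

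*SAP*

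**What the plan says.** SAP 8.4 defines the sensitivity analysis as "only including the participants who have received the study drugs per the protocol". It then gives one specific application: among participants on the Q2M injection schedule, PK data are left out of the summary statistics for those who "received first dose of the study drug (B/F/TAF) < 46 days of the last dose of CAB+RPV IM injection". The same section says the overall PK summary is presented as well. SAP 8.5 declares no departures from the protocol's PK analyses.

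The protocol times the switch relative to the next injection. Inclusion criterion 5 (Protocol 4.2) reads "Ability to receive B/F/TAF up to 7 days prior to the next scheduled dose of CAB+RPV"; the synopsis eligibility list reads "B/F/TAF to be given up to 7 days of next scheduled CAB+RPV IM injection". Inclusion criterion 4 also requires that the participant has "received at least one dose of CAB+RPV IM injection; no missed CAB+RPV injections".

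Two SAP provisions bear on the consequences. SAP 5.2 summarises and lists, by participant, the days between the last CAB+RPV dose and the first B/F/TAF dose. SAP 4.3 says "A by-participant listing will be provided for those participants who did not meet at least 1 eligibility (inclusion or exclusion) criterion".

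**The concern.** Plasma CAB and RPV after the switch are part of a secondary endpoint, and residual concentrations depend on time since the last injection. A sensitivity set described as protocol-compliant should select on the protocol's own timing rule. Three features raise doubt:

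- **No derivation.** The visible protocol text contains no 46-day limit, and SAP 8.4 does not explain the number.
- **Ambiguous wording.** The synopsis phrase gives no direction. Criterion 5 can mean that the window opens 7 days before the injection, or that 7 days before is the latest start. On the second reading there is no early limit at all, and the SAP rule would drop compliant participants.
- **No late limit.** Taken alone, the stated rule would keep a start on Day 70 or Day 100.

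If the rule and the label differ, a reader could take the sensitivity summary as evidence about on-protocol switchers when it covers a somewhat different group.

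**Working it through.** **Inputs.** Cut-off: 46 days (SAP 8.4). Allowance: 7 days (Protocol 4.2 and synopsis). CAB: 90% elimination in about 38 weeks, which is 38 × 7 = 266 days (Protocol 1.3). PK participants: 35 − 10 = 25 in North America, at least 20 evaluable (Protocol 4.1). Assumed because the documents do not state it: an injection interval *I* of 56 days (8 weeks) or 59 to 62 days (two calendar months).

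**Can 46 be reproduced?** If the window opens 7 days before the next injection, the earliest start is *I* − 7:

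| *I* (assumed) | *I* − 7 | Early days kept, (*I* − 7) − 46 | *I* − 7 − 7 |
|---|---|---|---|
| 56 | 49 | 3 | 42 |
| 59 | 52 | 6 | 45 |
| 60 | 53 | 7 | 46 |
| 61 | 54 | 8 | 47 |
| 62 | 55 | 9 | 48 |

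One 7-day allowance yields 46 only for an interval of 53 days. Two allowances yield exactly 46 for an interval of 60 days. Neither the 60 days nor the second allowance is stated. The Day 1 questionnaire (Protocol Appendix 11.4.3, question 7) does ask about "injections late or outside of the window when you were supposed to receive them", so an injection window exists, but its width is not given.

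**The Q2M expansion.** The Figure 1 abbreviations, the SAP abbreviation list and SAP 8.4 expand Q2M as twice monthly. Read literally as 14 or 15 days, 46 days would span about three intervals (46/15 = 3.1; 46/14 = 3.3) and the rule would make no sense. The interview guide and Day 1 questionnaire speak of 2 months, so the expansion is a clerical slip. It changes nothing in the calculation.

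**Size of the early side.** With log-linear decay, the fraction of CAB remaining after *d* days is 10^(−*d*/266). A start *d* days before the window opens has Day 1 CAB higher by 10^(*d*/266) − 1:

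- *d* = 3: 2.63%
- *d* = 9: 8.10%

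If the other participants start at window opening, one such person moves the mean by that excess divided by *n*: from 2.63%/25 = 0.11% to 8.10%/20 = 0.41%. Even if every participant started on Day 46, the mean would be at most 8.1% higher. Under the same decay assumption these percentages carry unchanged to Weeks 4, 12 and 24.

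**Size of the late side.** A start *d* days late lowers that person's Day 1 CAB by 1 − 10^(−*d*/266):

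- 7 days: 5.88%, which is 0.24% of the mean at *n* = 25 and 0.29% at *n* = 20
- 28 days: 21.5%, which is 0.86% and 1.08%

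RPV cannot be sized, because no elimination figure is given.

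**The case for a change.** The strongest case for changing the SAP is that a pre-specified flag should not rest on an unexplained number. SAP 2.1 reports the interim analysis of the North American participants as already conducted, and these are the only participants with PK samples. The documents do not say whether that interim included PK or whether the 46-day rule predates it. Writing down the derivation would cost a sentence. Listing a late starter as an eligibility failure under SAP 4.3 does not by itself remove that person from the sensitivity set.

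Part of this stands: the visible text does not derive 46 days, and a sentence on its origin and on late starts would help a later reader. The stronger claim, that early starters are wrongly kept, does not stand. It depends on an interval the documents do not state, it passes over the 60 − 7 − 7 construction, and the unseen Figure 1 may carry the limit. On late starts, the governing sentence of SAP 8.4 already confines the set to protocol-compliant dosing, and the 46-day clause can fairly be read as one application of it. A clearly late start would also fail the bar on missed injections, which should make such cases rare. The two 7-day wordings are better described as a loose synopsis line beside a fuller criterion than as a contradiction. Aligning them, along with the Q2M expansion, is document housekeeping for the sponsor; no view is taken here on which switch window is right.

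**Conclusion.** No change to the plan follows. This is missing detail that analysts can handle sensibly, plus a clerical slip over Q2M. Whether 46 days matches the protocol window cannot be settled from the visible documents: it does under an unstated 60-day interval with two 7-day allowances, and it does not if the window opens 7 days before an assumed 56- or 59-to-62-day due date.

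If it does not match, each disputed early starter shifts the mean Day 1 CAB by about 0.1% to 0.4%, and someone 28 days late by about 1%. These figures assume log-linear decay at the protocol's approximate 38-week figure and 20 to 25 PK participants. The number of people in the disputed days is unknown.

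The effect is confined to one descriptive summary with no hypothesis test. The overall PK summary and the co-primary safety endpoints are untouched. If criterion 5 sets a latest start and the rule drops compliant early starters, they still count in the overall summary. Individual gaps in days (SAP 5.2) and concentrations (SAP 8.3) are both listed, so anyone holding the listings can apply another cut-off.
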